Aging and Speech Perception in Complex Listening Environments
NCT03704142

2/28/2022

Study objectives

The goal of this study was to assess the effectiveness of, and benefits provided by, several over-the-counter, direct-to-consumer hearing devices. Specifically we were interested in assessing the benefits of these devices for middle-age people with no more than mild hearing loss. While some literature already exists on the effectiveness of devices of this type (Reed et al 2017, Cho et al 2019, Seol et al 2021, among others), these are primarily studies of individuals with greater degrees of hearing loss. Additionally, the goal of this study was to assess both the objective benefit of the devices, in terms of performance on a speech perception task, and to quantify subjective benefit in terms of self-rated listening effort while using the devices.

The study assesses four specific devices: Sound World Solutions CS50+, Nuheara IQ Buds, Tweak Focus, and Bose Hearphones. These four devices are all specifically classified as Personal Amplification Products, or PSAPs. Participants were randomly assigned to use one of these four devices during the study.

Study methods and procedures

The study consisted of three parts: intake procedures, where participants were given consent forms, performed cognitive and hearing assessments, and were fitted for the PSAP to which they were assigned; a speech perception task; and a brief post-test survey.

As part of the intake procedures, subjects completed the Montreal Cognitive Assessment (Nasreddine et al., 2005), after which audiometry and tympanometry were completed, and the subjects were fitted with a PSAP. Subjects were fitted binaurally, with suitable dome sizes and wire length selected to ensure an appropriate physical fit. Subjects assigned to the IQ Buds or CS50+ then performed an in-situ hearing test using the device's smartphone app. All devices were set to directional microphone mode (called 'focus', 'noisy', 'restaurant', and 'focused' for the IQ Buds, Tweak Focus, CS50+ and Hearphones, respectively) for the remainder of the time they were worn.

Verification of each PSAP was performed with the Audioscan Verifit 2 Speechmap system using an on-ear probe microphone to measure output. The International Speech Test Signal (ISTS) was used to obtain real-ear unaided responses (REUR) for 50 dB SPL input, followed by aided responses at 50 dB SPL and 65 dB SPL. The output of each device was adjusted so that the long-term average speech spectrum of the ISTS would approximate National Acoustic Laboratories Non-Linear 2 (NAL-NL2) targets within +/- 5 dB SPL where possible. For devices with limited fine-tuning ability, targets in the 1 kHz – 2 kHz range were given preference. To confirm loudness comfort, swept tones were presented from 0.25 – 8 kHz at 85 dB SPL, followed by pink noise at 80 dB SPL. Participants rated the above stimuli on a 7-point loudness scale (7 = uncomfortably loud). If participants rated either loudness test as a 7, gain was reduced and the loudness test was repeated until a comfortable loudness level was reached. In cases where gain was reduced following the loudness comfort test, aided responses to ISTS were re-measured with the final device settings to be used in the speech perception task.

In the speech perception task, subjects were played a series of sentences and instructed to repeat them back verbatim. The sentences were all taken from the same corpus, developed by Helfer, Merchant, and Freyman (2016). Sentences in this corpus all have the same syntactic structure: *Name found the color noun and the adjective noun here* (with the five underlined words denoting the target words which varied across sentences). A sample sentence is *Theo found the pink menu and the true item here*. All sentences were recorded from a female speaker. The subjects performed the task once while using a PSAP (aided) and once without (unaided), with different sets of sentences. Half of the

participants in each device group began with the unaided test block, and half with the aided; this factor was randomized within each device group. Their responses were audio-recorded and analyzed and scored off-line.

Subjects performed the task in a sound booth with three loudspeakers. Target sentences were played from a loudspeaker located directly in front of the participant and maskers were played from loudspeakers located 60 degrees to the right and left. Maskers were either speech-shaped steady-state noise (SSN), speech-shaped envelope-modulated noise (SEM), or sentences from the same corpus as the stimuli, also spoken by other female talkers. Masking sentences began at a random point in the sentence, with the beginning of the sentence appended to the end, in order to assist participants in segregating the target sentence (which always began with Theo, Victor, or Michael) from the masking sentences. Target presentation level and signal-to-noise ratio (SNR) were both varied as well: target sentences were presented at either 50 decibels A or 65 decibels A, and maskers were presented at levels corresponding to 0 decibels SNR and -6 decibels SNR.

Nine sentences (45 target scoring words) occurred in each of twelve auditory conditions (3 masker types by 2 presentation levels by 2 SNRs), all randomized within each block (aided vs. unaided), making 216 sentences across 24 total conditions. In addition, before each block, subjects were given 12 practice trials (four with each masker type) to become accustomed to doing the task with or without the device. Subjects were scored on the speech perception task in terms of percentage of correct target words accurately repeated in each condition.

At the end of each of the two blocks, subjects were asked to indicate how much effort they needed to expend to complete the task on a scale of 1 (very little effort) to 10 (a great deal of effort).

Participants also completed a brief survey after the speech perception task. This survey asked them to indicate the extent to which participants thought the device would be helpful in the real world; how willing they would be to use the device in the real world; whether they would recommend the device to others; and how comfortable they found wearing the device.

Statistical Analysis Plan

Dependent variables to be analyzed are performance on the speech perception task, benefit of use of the device, and self-rated listening effort. Performance will be measured as percent of target words accurately repeated; benefit will be measured as percent correct with device minus percent correct without device. Listening effort will be measured on ten-point scale (10 being the greatest effort, 1 the least).

Between-subjects variables to be measured are device (i.e., which of the four devices the participant used), age, and hearing loss (better-ear Pure Tone Average). Within-subject independent variables to be analyzed are device condition (i.e., with vs. without device) and acoustic properties of the stimuli: presentation level of target sentences (soft vs. loud), type of masking noise (SEM noise, SSN noise, or competing speech maskers), and signal-to-noise ratio (-6 dB or 0 dB).

Statistical analysis will be done with separate Repeated Measures ANOVAs for Performance, Benefit, and Self-Rated Effort. Responses to the post-experiment questionnaire will be analyzed qualitatively.

References

<https://doi.org/10.1001/jamaoto.2019.0667>.

Nasreddine, Z. S., Phillips, N.A., Bédirian, V., Charbonneau, S., Whitehead, V., Collin, I., Cummings, J. L. & Chertkow, H. (2005). The Montreal Cognitive Assessment, MoCA: A brief screening tool for Mild Cognitive Impairment. *Journal of the American Geriatrics Society*, 53, 695-699. <https://doi.org/10.1111/j.1532-5415.2005.53221.x>.

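### Does scoring the sentence-initial name, always one of three, distort the measured device benefit?

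*Combined protocol and SAP*

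**What the plan says.** The protocol's section on study methods and procedures gives a fixed frame, "Name found the color noun and the adjective noun here", "with the five underlined words denoting the target words which varied across sentences". It describes the target under competing speech as "the target sentence (which always began with Theo, Victor, or Michael". On quantity it says "Nine sentences (45 target scoring words) occurred in each of twelve auditory conditions", and on scoring "Subjects were scored on the speech perception task in terms of percentage of correct target words accurately repeated in each condition". One of the three maskers is "sentences from the same corpus as the stimuli, also spoken by other female talkers". Of the spoken responses it says "Their responses were audio-recorded and analyzed and scored off-line".

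The Statistical Analysis Plan defines performance on the same percentage of target words, and "benefit will be measured as percent correct with device minus percent correct without device". Its within-subject factors are device condition, presentation level, masker type and SNR. Word position is not a factor, and no score is planned with the name left out or for the name alone.

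**The concern.** The name differs from the other scored words in two ways. It has three alternatives, so it can be guessed or learned. Under competing speech it also marks which talker to follow, so one item is both cue and scored response.

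If the device's gain on the name differs from its gain on the other four words, the pooled benefit moves away from the four-word benefit. If that gap varies with SNR, level or masker, for instance because the name is near ceiling in easy conditions only, then a difference in benefit between conditions could partly reflect the name. These are contrasts that the planned ANOVAs examine.

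A related worry is that whoever scored the recordings may have known which block or device they came from. That could bias the same aided-minus-unaided difference.

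**Working it through.** **1. The plan's own counts.** 3 maskers × 2 levels × 2 SNRs = 12 conditions per block, and 12 × 2 blocks = 24. 9 sentences × 24 = 216. Both agree with the protocol. 45 / 9 = 5 scored words per sentence. The frame has exactly five varying slots (name, colour, noun, adjective, noun), so the name is scored. The underlining is lost in the text available here, but the count settles the point.

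**2. Weight of the name.** 9 / 45 = 20% in each of the 24 conditions, aided and unaided alike.

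**3. Effect on benefit.** Pooled benefit = 0.8 × (gain on the other four words) + 0.2 × (gain on the name). Dividing by the four-word gain gives 0.8 + 0.2r, with r = name gain / other-word gain.

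- r = 0: 0.80
- r = 1: 1.00
- r = 2: 1.20

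For r between 0 and 1 the attenuation is at most 20%. To go further one needs r. The documents give no accuracy by word position and no number of alternatives for the other four slots, and they do not say whether listeners were told the three names.

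**4. Illustration, all inputs assumed.** Every word gains 0.35 on the logit scale from the device. The name is 60% to 95% correct unaided, with a guess rate of 0 or 1/3.

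| Other words, unaided | Four-word benefit (points) | Pooled / four-word benefit |
|---|---|---|
| 45% | 8.7 | 0.83 to 0.98 |
| 10% | 3.6 | 0.88 to 1.24 |
| 5% | 1.95 | 0.94 to 1.62 |

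The direction depends on the assumed inputs.

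**5. Contrast between conditions.** Take the easier condition (other words 45%) minus the harder one (10%).

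- Four words: 8.7 − 3.6 = 5.1 points.
- Five words, name 95% (easier) and 60% (harder): 7.3 − 4.0 = 3.2 points with guess rate 1/3, and 7.3 − 4.5 = 2.8 points with guess rate 0 (differences taken before rounding). That is 63% and 54% of 5.1.
- Five words, name 85% and 75%: 3.7 to 3.8 points, or 72% to 74%.

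The model gives both conditions the same logit benefit. The 5.1 points therefore arise only from expressing that benefit as a percentage at two baselines. They are not a true contrast that the pooled score then loses. The contrast stays positive in every scenario.

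**6. What dropping the name would cost.** The binomial SE per condition at 50% correct, treating words as independent, is √(0.25/45) = 7.5 points on five words and √(0.25/36) = 8.3 on four. For an aided-minus-unaided difference, multiply by √2: 10.5 and 11.8. In the same model the five-word score has a larger word-level z:

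| Other words, unaided | Guess rate 1/3 | Guess rate 0 |
|---|---|---|
| 45% | 2% to 6% larger | 2% to 11% larger |
| 10% | 5% to 14% larger | 5% to 25% larger |

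**The case for a change.** The strongest case for the concern is that 0.8 + 0.2r is an identity, so the pooled and four-word benefits agree only when r = 1. Nothing guarantees that for an item with three alternatives. A constant offset would cancel between conditions, but a ceiling or floor on the name that varies with SNR or masker would not. Under competing speech a pooled score cannot separate selecting the right talker from understanding her. The remedy is also light: keep the five-word outcome, add a four-word sensitivity analysis and tabulate name accuracy by condition.

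The arithmetic and the limit on interpretation stand. They do not amount to an error. Any keyword score pools words of unequal difficulty, and the same could be said of colours against nouns. Under competing speech the protocol rotates the maskers so that listeners can pick out a target that opens with one of the three names. Catching that name is part of following the target talker, and counting it is defensible. A remedy that leaves the defined outcome untouched concedes that this outcome is acceptable.

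On scoring, the documents do not say whether the scorers could tell block or device. That is a missing detail, and it does not show that scoring was unmasked. Because scoring is described in the past tense, masking it now could mean scoring 216 sentences per participant again.

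**Conclusion.** The concern does not hold. The name is scored and carries 20% of every condition. But the protocol and SAP define one outcome consistently, with the same weight in both blocks, and no stated rule is shown to give a wrong result.

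The possible shift in benefit is 0.2 × (name gain − other-word gain). It is zero if the gains are equal, and a loss of at most 20% if the name's gain lies between zero and the other words' gain. Larger or upward shifts, and the 54% to 74% figures for the contrast, rest on assumed accuracies, guess rates and logit benefit that the documents neither support nor exclude. The sign of the contrast does not change in any scenario examined.

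A four-word score and a name tabulation would be informative extras, but their absence is a matter of preference. The conclusion would need another look if word-level data showed that the effect of SNR, level or masker on benefit depended on the name.

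### The plan does not say how sentence sets were allotted to the aided and unaided blocks, and its models include neither sentence set nor block order

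*Combined protocol and SAP*

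**What the plan says.** Under Study methods and procedures, each participant is tested "once while using a PSAP (aided) and once without (unaided), with different sets of sentences". On the two blocks, the text says that half the "participants in each device group began with the unaided test block, and half with the aided; this factor was randomized within each device group". No other balancing between blocks is described.

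On the material: "Nine sentences (45 target scoring words) occurred in each of twelve auditory conditions", and these were "all randomized within each block (aided vs. unaided), making 216 sentences across 24 total conditions". That describes randomisation inside a block. It does not say which set served the aided block. All sentences come from one corpus, and "Sentences in this corpus all have the same syntactic structure".

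Under Statistical Analysis Plan, "benefit will be measured as percent correct with device minus percent correct without device". The list of factors reads "Within-subject independent variables to be analyzed are device condition (i.e., with vs. without device) and acoustic properties of the stimuli", the latter being level, masker and signal-to-noise ratio. The between-subjects variables are device, age and hearing loss. Sentence set, sentence and block order are absent from both lists. Performance and Benefit each get a repeated measures ANOVA.

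**The concern.** Two things change between a participant's blocks: the device and the sentences. Balancing block order separates the device from practice and fatigue. It separates the device from the sentences only if the allotment of sets also does so, and the document is silent on that.

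Objective benefit from wearing a device is one of the stated study objectives, and the benefit score is a simple aided-minus-unaided difference. If set A is always aided and set B always unaided, every score contains the difficulty of A relative to B, whichever block came first. That offset does not shrink as participants are added, while the standard error does, so a larger study would be more likely to declare a spurious benefit or harm. The planned ANOVA has no term that could show it.

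**Working it through.** **Counts in the document.** 3 maskers x 2 levels x 2 SNRs = 12 conditions per block; x 2 blocks = 24; x 9 sentences = 216; 9 x 5 words = 45. All agree with the stated figures. Each block therefore has 216/2 = 108 sentences.

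**Bias under three allotments.** Take a true device effect of 0, set A easier than set B by d points, an assumed gain of o = 3 points in the second block, and half the participants in each order.

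- *Set tied to device condition (A always aided).* Aided first gives d - 3; unaided first gives d + 3. Mean = d. For d = 1, 2, 3 and 5 the bias is 1, 2, 3 and 5 points.
- *Set tied to block position (A always first).* Aided first gives d - 3; unaided first gives 3 - d. Mean = 0.
- *Sets crossed with device condition and order.* The four cells give d - 3, d + 3, -d - 3 and -d + 3. Mean = 0.

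Sets drawn at random for each participant also give an expected bias of 0.

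**Plausible size of d.** The document gives no between-sentence SD. Assume 10 to 20 points. For two sets of 108, SD of d = SD x sqrt(2/108) = SD x 0.136, which is 1.4, 2.0 and 2.7 points for SD 10, 15 and 20. For one 9-sentence condition the factor is sqrt(2/9) = 0.471, giving 4.7, 7.1 and 9.4 points.

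**Type I error if sets are tied to device condition.** The document gives no benefit SD and no sample size. Assume SD 8 and N = 40 to 80, and test mean benefit = 0 at two-sided 5%.

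- Averaging over the chance size of d: 2 x P(Z > 1.96 x s/sqrt(s² + SD_d²)), with s = 8/sqrt(N).
  - Sentence SD 10, N = 40: s = 1.265, SD_d = 1.361, ratio = 0.681, error = 0.18.
  - Sentence SD 20, N = 80: s = 0.894, SD_d = 2.722, ratio = 0.312, error = 0.54.
- Fixing d = 2 points: the error is 20% at N = 20, 35% at N = 40 and 61% at N = 80. Over benefit SD 5 to 10 and N 20 to 80 it runs from 14.5% to about 95%.
- A milder case by the first formula, sentence SD 5 and N = 20: s = 1.789, SD_d = 0.680, error about 7%.

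**Unmodelled variance in the unbiased cases.** Take 8 points as the benefit SD without set or order effects, and o = 3.

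- *Position-tied:* the two order groups have means ±(3 - d), which adds (3 - d)² to the variance. With d = 2 the SD is sqrt(64 + 1) = 8.1; with d = -2 it is sqrt(64 + 25) = 9.4.
- *Crossed, d = 2:* adds d² + o² = 4 + 9, so the SD is sqrt(77) = 8.8.
- *Random draws (set part only):* adds 1.36² to 2.72² = 1.9 to 7.4, so the SD is 8.1 to 8.5.

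**The case against.** The strongest reply is that this is a gap in reporting, not a demonstrated fault. A reader might infer that set and device are confounded in this study. The document does not support that: it says the sets differ and nothing about how they were allotted. The simple arrangement of one list first and the other second would make the stated order balancing balance the sets as well, with a bias of 0. This stands, and it is why the point is conditional.

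The material also argues for modest differences. There is one corpus, one sentence frame and 108 sentences per block, and the first of the five scored words is always one of three names. This makes a large d less likely, but it does not show that the sets are equivalent, and no equivalence data are given.

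A reader might also take the 4.7 to 9.4 points for a single condition as possible bias. That would require sentences to be fixed to conditions as well as to the device. The statement on randomisation within blocks can be read as assigning sentences to conditions at random, in which case those differences average out over participants.

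Finally, a reader might extend the problem to the comparison of devices. An offset shared by all four randomised groups cancels there, and largely so in the effects of age and hearing loss on benefit. The document names no primary contrast, so the device comparison may matter as much to the investigators as the overall benefit.

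**Conclusion.** The point holds in conditional form. Nothing in the document separates set difficulty from the aided effect, and neither set nor the already randomised block order is in the planned models. If sets were tied to device condition, the aided main effect and mean benefit carry a bias equal to the full set difference. Otherwise there is no systematic bias in mean benefit, and what remains is avoidable variance.

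The size cannot be fixed from the document. The 18% to 54% range should not be read as this study's error rate. It rests on an assumed sentence SD of 10 to 20 points, benefit SD of 8 points and N of 40 to 80, and on the least favourable allotment. Comparisons of benefit between devices are largely unaffected.

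**What to change.** 1. State how sentence sets were allotted to the aided and unaided blocks.
2. Add block order as a between-subjects factor in the Performance and Benefit ANOVAs. In the Performance model include its interaction with device condition, because that is where a second-block gain appears; in the Benefit model the main effect does this.
3. If the recorded set assignment varied across participants separately from order, add it in the same way. If sets followed block position, the order term already absorbs the set difference.
4. Use sentence as a random effect only in a trial-level model of Performance. It has no place in a model of the Benefit score, because the two blocks share no sentences.
5. If sets were fixed to device condition, say that the aided main effect and mean benefit include the set difference, and report any evidence that the sets are equivalent. No model term can separate the two in that case.
6. For any testing still to be done, cross the two sets with aided/unaided and with block order within each device group. The methods are written in the past tense, so this may no longer apply.

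The cost is one or two between-subjects degrees of freedom for the added factors and a little more analysis work. Crossing sets changes only the stimulus allocation list, with no extra participants or testing time.

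### Device comparisons use the raw aided-minus-unaided difference, which gives up precision where the unaided measurement is noisy (effort ratings, single conditions) but little or none in the overall contrast

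*Combined protocol and SAP*

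**What the plan says.** The Statistical Analysis Plan defines the benefit outcome as a simple subtraction: "benefit will be measured as percent correct with device minus percent correct without device". The models are "separate Repeated Measures ANOVAs for Performance, Benefit, and Self-Rated Effort". The between-subjects variables are device, "age, and hearing loss (better-ear Pure Tone Average"). They are listed as variables to be measured, and how age and hearing loss enter each model is not spelled out. The unaided score is not among them. It enters the Performance model only as one level of a repeated factor: "Within-subject independent variables to be analyzed are device condition (i.e., with vs. without device").

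Three design facts bear on the point, the first from Study objectives and the others from Study methods and procedures:

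- **Device is a randomised between-subjects factor.** "Participants were randomly assigned to use one of these four devices during the study".
- **Block order is counterbalanced.** Half of the "participants in each device group began with the unaided test block, and half with the aided", randomised within device group.
- **Outcomes differ in how much data they rest on.** "Nine sentences (45 target scoring words) occurred in each of twelve auditory conditions", whereas effort is a single 1-to-10 rating after each block.

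No sample size, power, SD or aided-unaided correlation is stated.

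**The concern.** Each participant wears only one device, so comparing devices is the between-person part of the design and has the least precision to spare. Subtraction fixes the coefficient on the unaided measurement at 1. If that measurement is noisy, the best coefficient is smaller, and subtraction carries the excess noise into the comparison. It also leaves part of any chance difference in unaided scores in the device contrast, so a group that happens to score low unaided tends to show more benefit.

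The Performance and Effort ANOVAs do not avoid this. In each, the device by aided/unaided interaction is the same difference-score contrast. What is at stake is precision that could be recovered from data the study already collects. Because the documents give no sample size or power, nothing in them shows that this precision can be spared.

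**Working it through.** **Inputs from the documents.** 45 words per condition; 12 conditions per block, so 12 x 45 = 540 words per block; one effort rating per block; four randomised devices; counterbalanced order. The plan has no power or precision figure to reproduce.

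**Assumed, because not in the documents.** The correlation rho between aided and unaided measurements, their SDs, the true between-person SD, and the number per device.

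**1. Variance, equal SDs (s).**
- Raw difference: 2s²(1 - rho).
- Adjusted for the unaided measurement: s²(1 - rho²).
- Ratio, adjusted to raw: (1 + rho)/2.

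| rho | ratio | extra participants the raw difference needs | shift in the raw contrast from a 5-point unaided imbalance, (1 - rho) x 5 |
|---|---|---|---|
| 0.5 | 0.75 | 33% | 2.5 points |
| 0.7 | 0.85 | 18% | 1.5 points |
| 0.9 | 0.95 | 5% | 0.5 points |

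With unequal SDs the excess variance of the difference is (s_unaided - rho x s_aided)². It is never negative, but it is zero when s_unaided = rho x s_aided. At rho 0.7, an unaided-to-aided SD ratio of 0.8 gives a variance ratio of 0.98, and an SD ratio of 1.25 gives 0.63.

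**2. What the word counts imply for rho.** At 50% correct the binomial variance is 2500/45 = 55.6 for one condition (SE 7.45 points) and 2500/540 = 4.63 for a block (SE 2.15 points). With no other noise, rho = SD²/(SD² + SE²). This is a ceiling: other noise lowers rho and raises the gain.

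| assumed person SD | rho, one condition | ratio | rho, whole block | ratio |
|---|---|---|---|---|
| 5 | 0.31 | 0.66 | 0.84 | 0.92 |
| 10 | 0.64 | 0.82 | 0.96 | 0.98 |
| 15 | 0.80 | 0.90 | 0.98 | 0.99 |

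So the gain is about 10% to 34% within one condition and about 1% to 8% overall.

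**3. Finite samples.** These large-sample ratios ignore the cost of estimating the slope. In a simulation of four groups with an order term and equal SDs, the ratios with 10 per device were 0.77, 0.87 and 0.98 at rho 0.5, 0.7 and 0.9. With 6 per device and rho 0.9 the ratio was 1.00. Both estimators were unbiased. Further simulations with 8 to 20 per device and assumed SDs gave ratios of 0.77 to 1.01 for separate single-condition models and about 0.89 to 1.04 for the overall contrast adjusted for the block mean. The effort comparison gained 5% to 32% at rho 0.4 to 0.8.

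**4. The covariate must match the contrast.** Take person SD 10 and binomial noise only. One slope pooled over same-condition scores is b = 100/(100 + 55.6) = 0.643. Applied to the overall contrast, the variance is (1 - b)² x 100 + (1 + b²) x 4.63 = 12.76 + 6.54 = 19.3. The raw difference has 2 x 4.63 = 9.26. The pooled slope therefore doubles the variance (19.3/9.26 = 2.08), because the 12-condition mean needs a slope near 1. In the simulations, which added other noise, the pooled slope changed this variance by between -5% and +100%.

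**5. Carry-over.** With an assumed 4-point carry-over from one device into a later unaided block, at rho 0.7 and 20 per device, the raw contrast was biased by -2.1 points and the adjusted one by -1.4.

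**The case against.** **The difference is a legitimate measure.** Study objectives asks how much benefit the devices give, and aided minus unaided estimates that directly. This stands, and it is why the point is confined to comparisons between devices.

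**The overall device contrast hardly suffers.** This also stands. With 540 words per block, differencing already removes most of any chance imbalance. At the ceiling values of rho for person SDs of 10 and 15, a 5-point unaided imbalance leaves about (1 - 0.96) x 5 = 0.2 and (1 - 0.98) x 5 = 0.1 points.

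**The unaided score is not a baseline.** Half of each device group gives it after wearing the device, and an order term does not remove device-specific carry-over. That is correct, but the raw difference needs the same assumption and was the more biased of the two in the carry-over check. The objection calls for stating the assumption; it does not favour the raw difference.

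**The gain depends on unknown SDs.** True: it disappears if s_unaided = rho x s_aided. The documents cannot settle this.

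**Stronger readings the documents do not support.** A reader might infer that the planned device comparison is biased or invalid. Randomisation protects it, absent device-specific carry-over. A reader might also carry the single-condition loss over to the main comparison, although that comparison averages 12 conditions. Nor can the comparison be called wholly unadjusted: age and better-ear hearing loss are listed, with an unclear role, though they do not replace the unaided measurement.

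**Conclusion.** The point holds as a matter of efficiency, for between-device comparisons only. The plan forgoes a cheap adjustment that would generally sharpen the effort comparison and contrasts within single conditions. With equal SDs the variance falls by 25% at rho 0.5 and 15% at rho 0.7. For the overall speech-score contrast the gain is small or nil: about 1% to 8% on binomial noise alone for person SDs of 5 to 15 points, and none with few participants per device.

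The direction follows from algebra. The size rests on assumed rho, SDs and numbers per device, none of which the documents give. The validity of either analysis rests on there being no device-specific carry-over, which the plan does not state.

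**What to change.** Amend the Statistical Analysis Plan for comparisons between devices:

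1. **Effort:** compare devices on aided effort, with unaided effort, block order, age and better-ear hearing loss as covariates.
2. **Within a condition:** model the aided score on device and that condition's unaided score, with a separate model for each condition.
3. **Overall contrast:** use the participant's block-mean unaided score as the covariate. Do not use one slope pooled over same-condition scores, which can increase the variance.
4. **Assumption and summary:** state that the comparison assumes no device-specific carry-over, because half of each group does the unaided block second. Keep aided minus unaided as the measure of each device's own benefit.

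The cost is SAP wording, a slightly more complex model and a few degrees of freedom. No new data are needed. Item 3 may bring little or no gain.

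### Does leaving open how age and hearing loss enter the three ANOVAs put the test of device benefit at age 0?

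*Combined protocol and SAP*

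**What the plan says.** The Statistical Analysis Plan names three outcomes: performance, benefit and self-rated effort. For benefit, "benefit will be measured as percent correct with device minus percent correct without device". It lists the between-subject variables ("Between-subjects variables to be measured are device (i.e., which of the four devices the participant used), age, and hearing loss (better-ear Pure Tone Average")) and then the repeated ones: "Within-subject independent variables to be analyzed are device condition (i.e., with vs. without device) and acoustic properties of the stimuli". The model is given in one clause: "separate Repeated Measures ANOVAs for Performance, Benefit, and Self-Rated Effort". No section says whether age and PTA enter all three models, in what form, with which interactions, or with which type of sums of squares.

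Two other places bear on the point. Study objectives sets the target group: "we were interested in assessing the benefits of these devices for middle-age people with no more than mild hearing loss". Study methods and procedures fixes the effort data at one rating per block: "At the end of each of the two blocks, subjects were asked to indicate how much effort they needed to expend". Device condition is therefore the only repeated factor that the effort analysis can have.

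**The concern.** The study's main question is answered by the device-condition effect in the performance and effort models, and by the overall mean in the benefit model. When continuous covariates are crossed with a repeated factor and effects are tested by Type III sums of squares, that effect is evaluated where every covariate equals zero. With raw age in years, this is a newborn. Such a test is an extrapolation far outside "middle-age people with no more than mild hearing loss". It could miss a real benefit, or report harm where the average participant gained. In a model without device-by-covariate terms, the rows for device by condition, age by condition and PTA by condition are the same under either coding, so they would not reveal the fault.

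**Working it through.** The documents give no sample size, no age or PTA summary and no power calculation, so the plan has no figure to reproduce. All numerical inputs below are assumptions.

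**1. Where the test sits.** Let *d* be a participant's aided minus unaided score. The device-condition test is the test of β₀ = 0 in

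*d* = β₀ + device (sum-to-zero coded) + β₁·age + β₂·PTA + error.

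With raw covariates, β₀ is the mean difference at age 0 and PTA 0. With centred covariates, it is the difference at the sample means.

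**2. Loss of precision.** With equal device groups, the variance of β₀ is σ²/N centred and σ²(1/N + m′S⁻¹m) raw, where m holds the covariate means and S is the within-device cross-product matrix. If age and PTA are uncorrelated,

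SE ratio ≈ √[1 + (mean age/SD age)² + (mean PTA/SD PTA)²].

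Take PTA mean 14 and SD 6 dB, so (14/6)² = 5.4. Take age as uniform, with SD = range/√12. The simulations used N = 40 to 80 and an age–PTA correlation of 0 or 0.4.

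| Age range | Mean / SD | Formula | Simulated |
|---|---|---|---|
| 30–70 | 50 / 11.55 | √(1 + 18.7 + 5.4) = 5.0 | 4.7–5.5 |
| 40–65 | 52.5 / 7.22 | √(1 + 52.9 + 5.4) = 7.7 | 7.6–8.3 |
| 45–60 | 52.5 / 4.33 | √(1 + 147.0 + 5.4) = 12.4 | 12.8–13.5 |

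Age does most of the damage. In the middle row it contributes 52.9 of the 58.3 added under the root. PTA 0 may lie near the sample, because near-normal hearing fits the target group.

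**3. Effect on the test.** With a true mean benefit of 5 points (SD 10) that does not vary with age or PTA, power was 0.86–0.99 centred and 0.05–0.16 raw.

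With zero benefit at the average age and a benefit slope of 0.2, 0.3 or 0.5 points per year (N = 60, ages 40–65), the raw test rejected in 17%, 33% and 69% of runs. The centred test rejected in 5–6%.

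The sign can also reverse. With a mean benefit of 4 points at age 53 and a slope of 0.3, the raw test targets 4 − 0.3 × 53 = −11.9. The share of trials significantly negative depends on the slope (N = 40, SD 8): about 3% at 0.1, 9% at 0.2, 22% at 0.3, 66% at 0.5, and none at −0.3.

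**4. What has to be true for this to happen.** One simulated data set (N = 60), raw against centred:

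| Specification | Tested effect | F, raw | F, centred |
|---|---|---|---|
| Type III, covariate × condition fitted | condition | 9.69 | 22.77 |
| Sequential sums of squares | condition | 22.77 | 22.77 |
| No covariate × condition term | condition | 21.01 | 21.01 |
| Type III, covariate × condition fitted | device × condition | 2.50 | 2.50 |
| Same, with device × age added | device × condition | 0.63 | 2.68 |

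The fault in the condition test appears only in the first row. If age and PTA are grouped, there is no zero point to extrapolate to. The last two rows show that the comparison between devices is immune to coding only when no device-by-covariate term is fitted.

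**5. Would it pass unnoticed?** In another simulated data set (N = 40), raw entry cut the presentation-level effect from F(1,34) = 111.8 (p < 0.001) to 1.87 (p = 0.18). Target levels differ by 65 − 50 = 15 dB, so a null result there is an obvious alarm. Benefit is a simple difference score, so its observed mean is also available to set against the model estimate.

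**The case for a change.** The best argument for a change is that the omission is real, nothing elsewhere fills it, and one unstated choice can decide whether the main test means anything. A few sentences would settle it, with no new data. Grouping is not free either: in simulation, median splits cut power for age by device condition from 87% to 66% (assuming an age–benefit correlation of 0.5). Crossing two such splits with four devices (16 cells) left an empty cell in 58% of samples of 40.

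The omission and the arithmetic stand. What does not follow is that the plan leads to the bad result. It names a repeated measures ANOVA and puts age and PTA in one list with a four-level factor, so grouping is at least as natural a reading as raw covariates. Nothing in the text points to the harmful combination. The loss from median splits is an ordinary cost of one permissible reading and affects secondary questions about age and hearing loss, not the test of average benefit.

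**Conclusion.** The plan leaves a minor part of the model unwritten; it does not state a rule that gives a wrong result. The harm is conditional on continuous entry, no centring, covariate-by-condition terms and Type III tests all together. Given those, a standard error 4.7 to 13.5 times the centred one is a fair range, but it rests wholly on assumed sample sizes and age and PTA distributions. The sign-reversal rates rest further on an assumed positive slope of benefit on age. Grouping, centring, sequential testing, or omitting the covariate-by-condition terms each removes the problem. An analyst who did enter raw covariates would have plain warnings in the output. The remaining choices, including the single repeated factor for effort, follow from the data structure or from ordinary practice. No change to the plan is called for.
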